Evidence that these biomarkers are mediators of pregnancy outcomes that are affected by smoking has important implications for other pharmacotherapy studies in pregnant smokers by providing surrogate measures of potential risk [46] or in studies of reduced-exposure products (e.g., e-cigarettes, smokeless tobacco) that may be used by pregnant women. Since the FDA has recently been authorized to regulate tobacco products [56] there is likely to be heightened interest in biomarkers of tobacco product risk, particularly in vulnerable populations.

3. Hypotheses, aims and objectives:

Hypothesis 1:

We hypothesize that the nicotine inhaler compared to placebo inhaler will double the 7-day point prevalence abstinence rates (confirmed by exhaled CO) at 32-34 weeks gestation and will reduce the number of cigarettes smoked per day (CPD).

Aims / objectives 1:

To examine the efficacy of the nicotine inhaler compared to a matched placebo for smoking cessation and reduction among pregnant smokers.

Hypothesis 2:

- a) The nicotine inhaler will yield lower cotinine concentrations than placebo at 32-34 weeks gestation.
- b) Infants born to mothers in the NRT group will have higher birth weights and greater gestational age than infants born to mothers randomized to placebo. 2c) Fewer nicotine-treated subjects will deliver a low birth weight (<2500 grams) or a preterm (<37 weeks) infant than those in the placebo group.

Aim/Objective 2:

To compare the nicotine inhaler with placebo on safety measures which include a) overall nicotine exposure (i.e., serum cotinine) and b) birth outcomes (i.e., birth weight and gestational age).

Hypothesis 3: Pregnant women who are heavier smokers (i.e., ≥ 10 cigarettes/day) will be less able to quit with behavioral treatment alone than lighter smokers and the inhaler will increase cigarette abstinence more in heavier smokers.

Aim/Objective 3: To identify factors that determine which women benefit most from the use of nicotine inhaler for smoking cessation during pregnancy

Hypothesis 4: We hypothesize that birth weight will be negatively correlated with CPD and exhaled CO at the end of pregnancy, and that smoking cessation or reduction in the third trimester will explain the effect of treatment group on birth weight. We will also explore the interrelations among birth outcomes, tobacco exposure, and other promising biomarkers.

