Specific Aim 2.a: To compare effects of the nicotine inhaler with placebo on overall nicotine exposure (i.e., measured as serum cotinine), and birth outcomes [i.e., birth weight, gestational age, % of subjects who deliver a LBW (<2500 g) or preterm (<37 wk gestation) infant]. We will use a linear mixed model (see above) to determine whether cotinine concentration changes differentially over time by treatment group.

Specific Aim 2.b: Birth Outcomes. Mean birth weight will be compared for treatment groups using a two-sample t-test, or analysis of covariance if necessary to adjust for imbalances in patient characteristics. We will also compare the percentage of subjects in each group who deliver an infant of LBW (1500-2500 g) or preterm delivery using chi square or logistical regression.

Specific Aim 3: To determine which subjects benefit most from NRT, we will use logistic regression to examine the following predictors of treatment response (i.e., smoking cessation at 6 or 32 wks

Nicotine Replacement for Smoking Cessation during Pregnancy

gestation): pretreatment CPD, FTND score, perceived stress, motivation to quit, self-efficacy, treatment group, and the interaction of treatment group and the other independent (i.e., potential moderator) variables. **Analyses:** First, we will use a stepwise procedure to choose predictor variables and interaction terms that are significant ($\alpha=0.05$). A significant interaction between treatment group and other variables (e.g., pretreatment CPD) implies that the regression coefficients for this variable are not homogeneous with respect to the efficacy of the medication. The Johnson-Neyman procedure [79], which yields values of the continuous moderator variable at which the treatment groups differ significantly on the dependent variable, will be used to determine the “break point” nicotine inhaler efficacy. In our completed study[1], the effect of nicotine gum appeared to depend on CPD during the pretreatment period. For light smokers, the cessation rates were 18% and 21% for the control and nicotine groups, respectively, while for heavy smokers the rates were 0% and 15%, respectively. Since a similar effect in a sample of 150 women would provide power=0.80, using a two-sided $\alpha=0.05$, our proposed sample of 360 pregnant smokers will provide more than adequate power to detect the effect.

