Dispensing and reconciliation: The study medication will be dispensed by the research nurse at baseline, Visit 2, and Visit 4 . At or before the baseline visit, the study nurse will fax key variables for a given subject to the research pharmacist at UCONN who will enter these variables into a specially developed computer algorithm. Once the pharmacist enters these variables into the computer program, the computer assigns a treatment assignment. The pharmacist will communicate with the study nurse (by fax or e-mail) which medication box # to dispense to the subject. Boxes of nicotine and placebo inhaler will be labeled with a study number, kept at study sites in a locked filing cabinet (with a daily temperature log) in a research room or research pharmacy depending on the site.

Reconciliation: At every visit, subjects are asked to return used cartridges and unused medication. Used cartridges will be validated with patient reports of study records of use. Unused medication will be sent back to pharmacy where it will be destroyed.

2. *Provide a description of known adverse events due to the intervention and the plan to deal with such adverse events (e.g. does reduction, removal of device, removal from trial.):*

A. Potential Risks:

The potential risks for subjects include blood drawing, psychological tests, breach of confidentiality, and risk of medication (adverse effects and serious adverse events and increased nicotine exposure). Medical histories will be reviewed prior to entry into the study at screening and subjects will be under medical supervision while in the study. Trained phlebotomists will draw all blood samples. Blood drawing may result in slight discomfort, bruising, or there may be soreness at the puncture site. In some instances, dizziness or fainting may occur.

It is not known which of the adverse pregnancy outcomes associated with cigarette smoking may be a result of nicotine. These adverse effects include 1) spontaneous abortion; 2) preterm delivery; 3) low birth weight; 4) preterm delivery or preterm premature rupture of membranes; 5) placenta abruption and placenta previa; 6) sudden infant death syndrome.

In phase 3 studies, the most common side effects with nicotine inhaler include cough, throat irritation, rhinitis and mouth irritation. We expect that these side effects will also occur in our population.

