We do not foresee withdrawing any subject from the study (since it is important to have as much information as possible in an efficacy and safety study), but may withdraw study drug if a subject is noncompliant or has a serious adverse event, or if they are still smoking after 6 weeks of treatment. If a participant either withdraws from the study or the investigator decides to discontinue a participant due to SAE, the participant will have appropriate follow-up medical monitoring. Monitoring will continue until the problem requiring hospitalization was resolved or stabilized with no further change expected, is clearly unrelated to study medication, or results in death.

4. Describe any stopping rules for the study:

The stopping rules will be established at the first DSMB meeting, and agreed upon by both the investigative team and the DSMB. We propose to place particular emphasis was made on monitoring of overall serious adverse events, nicotine exposure, and efficacy rates. We propose that the board review serious adverse events by treatment group on an ongoing basis (approximately twice a year or more or less often depending on subject accrual). As in our previous study, a table will be provided to the board with treatment groups designated as "A" and "B" in order to maintain study medication assignment blinding. The 4 types of events are (1) perinatal mortality (includes stillbirths, miscarriage after 28 weeks gestation, infant death), (2) spontaneous abortion (i.e., miscarriage prior to 28 weeks gestation), and (3) low birth weight (LBW) and (4) preterm delivery and (5) any other serious adverse events. General stopping rules proposed include 1) A significantly higher rate of subjects have low birth rates or other serious adverse events in group "A" or "B"; 2) determination that the increased incidence is related to study medication; 3) the emergence of unexpected serious adverse experience of unexpected serious adverse experience not specified in the study; 4) the board may recommend to stop the study after review of efficacy data once half the subject have been recruited if it appears to be little chance that a difference in efficacy will be observed between the 2 groups.

Nicotine Replacement for Smoking Cessation during Pregnancy

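### No planned final analysis counts fetal loss or infant death, so the Aim 2.b birth-outcome comparison could favour the inhaler if treatment affects loss

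*Combined protocol and SAP*

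**What the plan says.** Aim 2 is the trial's safety aim, and its birth measures are birth weight and gestational age. Hypothesis 2c reads: "Fewer nicotine-treated subjects will deliver a low birth weight (<2500 grams) or a preterm (<37 weeks) infant than those in the placebo group".

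The analysis is in Method(s) of data analysis, Specific Aim 2.b: "Mean birth weight will be compared for treatment groups using a two-sample t-test, or analysis of covariance if necessary", followed by "We will also compare the percentage of subjects in each group who deliver an infant of LBW", with LBW given there as 1500-2500 g, or preterm delivery. The test is chi-square or logistic regression. Nothing there says whether the percentage is of all randomised women or of deliveries, or how a miscarriage or stillbirth is classed. The other aims in that section do not mention fetal loss or infant death.

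Elsewhere the plan does recognise loss. Appendix A, item 2.A (Potential Risks) says it is not known which smoking-related outcomes may be due to nicotine, and begins the list "1) spontaneous abortion; 2) preterm delivery; 3) low birth weight". Appendix A, item 4 (stopping rules) gives the DSMB event types as "1) perinatal mortality (includes stillbirths, miscarriage after 28 weeks gestation, infant death), (2) spontaneous abortion (i.e., miscarriage prior to 28 weeks gestation", then LBW, preterm delivery and other serious adverse events. It adds: "We propose that the board review serious adverse events by treatment group on an ongoing basis", about twice a year, with the groups labelled A and B.

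**The concern.** With entry at 13-26 weeks, a woman can be randomised and then lose the pregnancy. Under the DSMB definition a miscarriage before 28 weeks is a spontaneous abortion, and that woman has no LBW or preterm infant to count. The planned birth comparisons therefore depend on the pregnancy surviving, which happens after randomisation and which treatment may affect. If the inhaler raised the loss rate, some pregnancies headed for a poor birth outcome could leave the LBW and preterm counts and the birth-weight mean. The reported birth outcomes would then look better on inhaler for a reason that is not a benefit. Aim 4 would go on to look for mediators of the birth-weight difference.

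The LBW definition adds to this. Read literally, the 1500-2500 g band in Aim 2.b also leaves out infants below 1500 g, whereas Hypothesis 2c and Aim 2.a use below 2500 g.

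**Working it through.** **The plan's own figure.** The sample size section gives 14.9% versus 26.9% quitting, 180 per arm, two-sided 0.05, power 0.80. The pooled proportion is 0.209. The standard error is √(0.209 × 0.791 × 2/180) = 0.0429 under the null and √((0.149 × 0.851 + 0.269 × 0.731)/180) = 0.0424 under the alternative. Power = Φ((0.12 − 1.96 × 0.0429)/0.0424) = 0.80. This reproduces and fixes the arm size at 180. No power is stated for LBW, preterm delivery or loss.

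**Inputs for the illustration.** The LBW rate without treatment effect is 18%, from the placebo arm of the completed gum trial (16/87, Table 1), with 10% as an assumed alternative. Placebo loss is assumed to be 2% (4 of 180) and inhaler loss 2 to 10 points higher. The inhaler is assumed to have no true effect on LBW risk. All p-values are uncorrected chi-square.

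**(a) Losses unrelated to LBW risk, 18% LBW rate.**
- All randomised as denominator: LBW is 0.18 × 176/180 = 17.6% on placebo. On inhaler it is 17.3% with 7 losses, 16.9% with 11 and 0.18 × 158/180 = 15.8% with 22. The largest bias is 17.6 − 15.8 = 1.8 points.
- Deliveries only: 18% versus 18%, no bias.
- Loss counted with LBW: 19.8% versus 21.2%, 23.0% and 28.0%.

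**(b) Worst case: every loss would have been LBW.** 18% of 180 is about 32 women per arm, from whom the losses are subtracted.

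| Losses, placebo v inhaler | LBW, all randomised | LBW, deliveries only | LBW or loss | Loss alone, p |
|---|---|---|---|---|
| 4 v 7 | 28/180 = 15.6% v 25/180 = 13.9%, p=0.66 | 28/176 = 15.9% v 25/173 = 14.5%, p=0.70 | 17.8% v 17.8% | 0.36 |
| 4 v 11 | 15.6% v 21/180 = 11.7%, p=0.28 | 15.9% v 21/169 = 12.4%, p=0.35 | 17.8% v 17.8% | 0.065 |
| 4 v 14 | 15.6% v 18/180 = 10.0%, p=0.11 | 15.9% v 18/166 = 10.8%, p=0.17 | 17.8% v 17.8% | 0.016 |
| 4 v 18 | 15.6% v 14/180 = 7.8%, p=0.02 | 15.9% v 14/162 = 8.6%, p=0.04 | 17.8% v 17.8% | 0.002 |

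At a 10% LBW rate (18 women per arm), 4 versus 14 losses is enough: 14/180 = 7.8% versus 4/180 = 2.2%, p=0.016.

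**Mean birth weight.** Assume a mean of 3100 g, and that a fraction L of inhaler infants who would have weighed w is lost. The mean rises by (3100 − L·w)/(1 − L) − 3100. With L=1% and w=1500 g this is (3100 − 15)/0.99 − 3100 = 16 g. With L=4% and w=800 g it is (3100 − 32)/0.96 − 3100 = 96 g. For scale, the plan cites about 300 g from the gum trial and 186 g from the patch trial. If losses are unrelated to birth weight, the shift is zero.

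**Power for loss alone, 180 per arm.** 2% versus 4%: Φ((0.02 − 1.96 × 0.0180)/0.0180) = 0.20. By the same formula, 2% versus 6% gives 0.49.

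**The case against.** The strongest reply is that fetal loss is already compared by arm. The DSMB sees stillbirth, miscarriage and infant death by group about twice a year, and a proposed stopping rule covers a significantly higher rate of serious adverse events in either group. In the worst-case rows where LBW shows a nominally significant false benefit, the loss comparison is itself significant (18 versus 4, p=0.002), so the board should see the harm. This stands, and a reader who infers that fetal loss is counted nowhere would be wrong. But it is interim monitoring. Its rules are to be settled at the first DSMB meeting, have no numeric boundary and are described as guidelines, with statistics supplied if requested. It commits to no final estimate or interval.

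A reader might also infer that the plan scores a loss as a good outcome. The documents do not say so. A loss is a non-event only if all subjects are the denominator; among deliveries it drops out. A stillbirth before 37 weeks might even count as a preterm delivery. The plan is silent on all three points.

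Nor do the documents say that losses fall mainly in pregnancies that would have been LBW or preterm. The entry criteria exclude threatened abortion, multiple gestation and known congenital abnormality. They give no loss rate and no support for that assumption, so a claim that a harmful inhaler would look protective goes too far.

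Lastly, the plan refers to a data and safety monitoring plan that is not a separate document in the file. A final comparison of losses might be set out there.

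**Conclusion.** The gap is real but moderate. No final analysis in the analysis section counts fetal loss or infant death, and the Aim 2.b comparisons have neither a denominator nor a rule for losses. If the inhaler affected loss, bias in its favour is possible.

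The size rests on assumed loss rates. With losses unrelated to LBW risk, it is nil among deliveries and at most 1.8 points among all randomised women. If every loss would otherwise have been LBW, a nominally significant false benefit needs about 6 points of excess loss at a 10% LBW rate, or about 8 points at 18%. Smaller excesses could still flatter the estimate (15.6% versus 11.7% with 11 versus 4 losses) and would be hard to establish from loss alone.

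A reader might conclude that a composite should become the main safety comparison. The table argues against that: in the worst case it reads 17.8% in both arms at every level of excess loss, and so conceals an excess of deaths.

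**What to change.** In Specific Aim 2.b:

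1. Use all randomised women as the denominator for LBW and preterm delivery, and define LBW as below 2500 g, as in Hypothesis 2c and Aim 2.a. State in advance how a miscarriage and a stillbirth are classed for each outcome. Show women with an untraced birth outcome separately, so that they are not counted as non-events.
2. Add fetal loss after randomisation and infant death by arm as a final comparison of their own, with risk difference and 95% CI and a stated time window. The denominator alone does not cure the problem, because a loss is still a non-event for LBW. The loss figures must therefore appear beside the LBW, preterm and birth-weight results.
3. Add, as a supportive analysis only, a composite counted once per woman: fetal loss, neonatal death, LBW or preterm delivery. Always show it with its components.

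The cost is SAP wording. The events are already needed for the DSMB table, though pregnancy outcome should be a named item in the birth chart review, which now lists infant measures and a general entry for other rare events. The drawback is one or two more reported outcomes, with low power for loss alone, so that result should be read as an estimate with its interval and a non-significant p-value should not be taken as reassurance.

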A.1. Importance of the Problem: Cigarette smoking during pregnancy is one of the most important modifiable causes of poor pregnancy outcomes in the United States [8, 9]. Although maternal smoking increases the risk of spontaneous abortion, placental complications, preterm delivery, and fetal and neonatal death, the most consistent effect is low birth weight (LBW, i.e., <2500 grams) [8, 10, 11]. Maternal smoking doubles the risk of delivering a LBW neonate [12]. LBW neonates, particularly those weighing <1500 g, have exponentially greater morbidity and mortality than normal weight infants [13]. In the US, maternal smoking is responsible for 30% of LBW babies, 10% of premature deliveries, and 5% of all infant deaths [14]. Nicotine affects nervous system development in animal studies, and similar effects have been observed in babies born to women who smoke. Smoking cessation during pregnancy has numerous health benefits; by 16 weeks gestation [15, 16], or even as late as the third trimester [16], cessation results in a near-normal birth weight infant. Smoking reduction also has beneficial effects on birth weight [17]. Because smoking has serious health risks for the mother and infant, robust efforts are needed to help pregnant women quit smoking.

Despite the risks, the majority of women who are smoking when they become pregnant continue to smoke throughout pregnancy. Women who quit smoking usually do so before their first prenatal visit and women who smoke into the second trimester are much less likely to quit [18]. These women are more likely to be single, heavier smokers (>1/2 pack per day), and to have a partner who smokes [19, 20]. Less educated women with greater nicotine dependence are particularly likely to continue smoking during pregnancy [19].

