A.2.b Efficacy studies of medications for smoking cessation during pregnancy: Placebo-controlled RCTs are the “gold standard” to assess the safety and efficacy of medications for smoking cessation. Two efficacy studies of NRT with sufficient sample size have been conducted in pregnancy [1, 7]. In a Danish study, all women received counseling by a nurse midwife and either 6 weeks of a nicotine patch (15 mg/16 hours) or a matching placebo [7]. At the end of pregnancy, neither quit rates (28% vs. 25%, respectively) nor the mean number of CPD (7.2 vs. 7, respectively) differed between the groups. However, patch compliance was poor (i.e., the average use being only 2 weeks), which may have reduced quit rates. The authors noted that the Danish Medical Authority advised against NRT use during pregnancy, and this national recommendation may have influenced compliance with treatment in their study. Importantly, however, the mean birth weight was 186 grams (95% CI 35-336) greater in the nicotine group than in the placebo group.

In another placebo-controlled RCT, we recruited 194 pregnant smokers from prenatal clinics to participate in a randomized trial of 2 mg gum or placebo for smoking cessation [1]. Participants received individualized behavioral counseling and were assigned to receive either 2 mg nicotine or placebo gum for 6 weeks followed by a 6-week taper. Biochemically-validated smoking cessation rates were non-significantly higher in the nicotine group at major endpoints (after 6 weeks: 13% vs. 9.6%, p= 0.45 and at 32-34 weeks gestation: 18% vs. 14.9%, p= 0.56). Importantly, nicotine produced a greater reduction in CPD and cotinine concentrations than placebo. There was also better treatment retention in the nicotine vs. placebo group. Mean (SD) birth weight and gestational age were also significantly greater in the nicotine group than in the placebo group [3287 g (569) vs. 2950 g (657); p<0.001 and 38.9 wk (1.7) vs. 38.0 wk (3.3); p=0.014, respectively]. Further, the most striking difference between treatment groups was the greater incidence of babies with LBW and preterm delivery in the placebo group compared with the nicotine gum group (Table 1).

Table 1: Serious Adverse Events in the Nicotine and Placebo Groups

	Placebo (N=87)	Nicotine (N=97)	P-Value
Low Birth Weight			
<2500 grams	16 (18 %)	2 (2%)	<0.001
Very Low Birth Weight			
<1500 grams	4 (5 %)	1 (1%)	0.19
Preterm Delivery	16 (18 %)	7 (7.2%)	0.027
Newborn Death	2 (2 %)	1 (1%)	0.60

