10. Counseling (10 Minutes): Counseling will focus on achieving or maintaining abstinence (set another quit date if necessary), increasing self-efficacy, skills training (depending on the patient's smoking status), and providing social support, and using inhaler to combat urges to smoke).
11. Serum will be sent for cotinine analysis only if the nurse identifies that the subject has significantly changed her smoking and/or inhaler use patterns (see DSMP for cotinine monitoring).

This visit will take 45 minutes.

Visit 6 (32-34 weeks gestation). The following items will be assessed by research nurse.

1. Vital signs and weight
2. Exhaled CO measurement

Nicotine Replacement for Smoking Cessation during Pregnancy

3. Nicotine Use Survey
4. Questionnaires: MNWS, PHQ
5. Adverse Effects Inhaler & Adverse Events
6. Concomitant Medication
7. Inhaler usage: We will collect used cartridges from patient and review diary of inhaler usage.
8. Maternal Blood Draw (15 cc) If possible, this blood draw will be incorporated with other routine prenatal blood draws. Will collect urine, if necessary.
9. Counseling (10 Minutes): Counseling will focus on achieving or maintaining abstinence (set another quit date if necessary), increasing self-efficacy, skills training (depending on the patient's smoking status), and providing social support, and using inhaler to combat urges to smoke).
10. Serum will be sent for cotinine analysis only if the nurse identifies that the subject has significantly changed her smoking and/or inhaler use patterns (see DSMP for cotinine monitoring).

This visit will take 45 minutes.

Birth outcomes: the research nurse or study coordinator will collect birth outcomes by chart review. Permission to conduct chart review for labor and delivery records will be included in the informed consent form. Information to be collected includes: Apgar scores, birth weight, infant sex, gestational age, head circumference, NICU admission, and infant length of stay. Other rare events associated with tobacco use during pregnancy and maternal medical conditions will also be recorded. Time to collect birth outcomes is estimated at 30 minutes.

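### The Aim 2.b test sentence gives low birth weight as 1500-2500 g, while the hypothesis and every other definition say <2500 g

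*Combined protocol and SAP*

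**What the plan says.** Section A.1 gives the definition: "the most consistent effect is low birth weight (LBW, i.e., <2500 grams". It treats infants under 1500 g as the most severe part of that group: "LBW neonates, particularly those weighing <1500 g, have exponentially greater morbidity and mortality than normal weight infants".

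Table 1 (section A.2.b), from the sponsor's earlier gum trial, has an LBW row labelled <2500 g and a further row headed "Very Low Birth Weight" for <1500 g.

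Hypothesis 2c reads: "Fewer nicotine-treated subjects will deliver a low birth weight (<2500 grams) or a preterm (<37 weeks) infant than those in the placebo group". In the analysis section, Specific Aim 2.a names the outcome as the percentage "of subjects who deliver a LBW (<2500 g) or preterm (<37 wk gestation) infant".

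Specific Aim 2.b, the next paragraph, then compares the "percentage of subjects in each group who deliver an infant of LBW (1500-2500 g) or preterm delivery" by a chi-square test or logistic regression. No other sentence names a test for the LBW proportion. The stopping rules in Appendix A, item 4 list LBW among the events for the DSMB, with no cut-off and no named test.

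**The concern.** The hypothesis and the sentence that tests it define the outcome differently. An analyst who programs from Aim 2.b would not count infants under 1500 g as LBW events. These are the infants that section A.1 singles out for the worst prognosis. The plan does not say whether they would be non-events or leave the denominator, and the analysis section has no separate <1500 g category to receive them. While both definitions stand, the choice between them could be made after the results are known.

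A second, weaker point is that LBW and preterm delivery are joined by 'or', so the sentence could be read as one composite outcome. On that reading an infant under 1500 g still counts if born before 37 weeks.

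**Working it through.** **Definitions side by side**

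| Place | LBW definition |
|---|---|
| A.1 Importance of the Problem | <2500 g |
| Table 1 (A.2.b) | <2500 g, with <1500 g as a further row |
| Hypothesis 2c | <2500 g |
| Specific Aim 2.a | <2500 g |
| Specific Aim 2.b (names the test) | 1500-2500 g |
| Appendix A, item 4 (DSMB) | no cut-off |

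**Inputs, all from Table 1.** Placebo N=87: 16 infants <2500 g, of whom 4 were <1500 g. Nicotine N=97: 2 infants <2500 g, of whom 1 was <1500 g. The subtraction below assumes that the <2500 g row includes the <1500 g row, as its label implies.

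**Reproducing the printed p-values.** For 16/87 v 2/97, the Pearson chi-square without continuity correction is 184 × (16×95 − 2×71)² / (87×97×18×166) = 13.86, p=0.0002 (Fisher exact 0.0002). Table 1 prints <0.001. For 4/87 v 1/97, Fisher exact gives 0.19, as printed.

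**Applying the 1500 g floor.** Placebo 16 − 4 = 12; nicotine 2 − 1 = 1. Events dropped: (4+1)/(16+2) = 5/18 = 28% (exact 95% CI 9.7% to 53.5%).

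Risk difference = p₁ − p₂, with Wald limits ± 1.96 × √(p₁q₁/n₁ + p₂q₂/n₂). Relative risk = p₂/p₁ (nicotine over placebo).

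| Definition | Placebo | Nicotine | Risk difference, points (95% CI) | Relative risk (95% CI) | Chi-square p |
|---|---|---|---|---|---|
| <2500 g | 16/87 (18.4%) | 2/97 (2.1%) | 16.3 (7.7 to 24.9) | 0.11 (0.03 to 0.47) | 0.0002 |
| 1500-2500 g, <1500 g as non-events | 12/87 (13.8%) | 1/97 (1.0%) | 12.8 (5.2 to 20.3) | 0.07 (0.01 to 0.56) | 0.0007 |
| 1500-2500 g, <1500 g out of denominator | 12/83 (14.5%) | 1/96 (1.0%) | 13.4 (5.6 to 21.3) | 0.07 (0.01 to 0.54) | 0.0006 |

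The risk difference shrinks while the relative risk moves further from 1, so the floor does not bias the result consistently in one direction.

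**Composite reading.** An infant under 1500 g is lost only if born at 37 weeks or later. The loss is therefore between 0 events (all five preterm) and 5 (none preterm). The documents do not give the cross-tabulation.

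**Power.** The plan states none for the LBW proportion. With n=180 per arm and two-sided α=0.05, power = Φ{[|p₁ − p₂| − 1.96√(2p̄q̄/n)] / √[(p₁q₁ + p₂q₂)/n]}. At the gum-trial rates it is 99.9% for <2500 g and 99.7% for 1500-2500 g. The smaller effects below are assumptions: the gum-trial placebo rate, with the same relative reduction under both definitions.

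| Assumed relative reduction | Power, <2500 g | Power, 1500-2500 g |
|---|---|---|
| 50% | 72% | 58% |
| 40% | 50% | 39% |
| 30% | 30% | 23% |

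If the relative effect differed above and below 1500 g, this pattern need not hold.

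**The case against.** The strongest reply is that the document largely settles the matter itself. Hypothesis 2c and Aim 2.a, the paragraph directly above, both give <2500 g, and harm requires an analyst to prefer one parenthesis to both. On the only data available the test stays significant, no stated sample size or power figure rests on the cut-off, and the illustration turns on five infants and, with the floor, a single nicotine-arm event. All of that stands, and it limits the weight of the point. It does not remove the error, because the odd parenthesis sits in the sentence that specifies the test.

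A deliberate split into LBW and very low birth weight is not a convincing defence. Table 1 shows the <1500 g row in addition to an LBW row labelled <2500 g, and the analysis section provides no <1500 g outcome.

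The composite reading is thin. The same 'or' appears in Hypothesis 2c and Aim 2.a, section A.2.b speaks of "the greater incidence of babies with LBW and preterm delivery in the placebo group compared with the nicotine gum group (Table 1", and Appendix A, item 4 numbers LBW and preterm delivery as separate event types. The clause requested on this is a clarification, not the correction of an error.

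**Conclusion.** The inconsistency is real and minor. Aim 2.b as written does not test Hypothesis 2c, and with LBW as its own outcome it would have left out 5 of 18 LBW events in the gum trial without changing significance there. That count rests on Table 1's rows being nested and on small numbers. The effect is confined to one dichotomised birth outcome. The comparison of mean birth weight has no 1500 g floor, and nothing shows that the range governs the DSMB's review. That the range is a slip is an inference from the other four definitions; the documents do not confirm it.

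**What to change.** Before unblinding, change the range in Specific Aim 2.b to <2500 g, in line with Hypothesis 2c and Aim 2.a, and add a clause that LBW and preterm delivery are compared as two separate outcomes. If a severity breakdown is wanted, report <1500 g as an additional category, as Table 1 does. The cost is one phrase and one clause. The chart review already covers what is needed ("Information to be collected includes: Apgar scores, birth weight, infant sex, gestational age"), so there is no new data collection and no operational change.
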